Baseline: Participants sign on to Zoom via the link provided during their assigned timeslot. Upon signing into the Zoom meeting, the research assistants provide a link (using the chat function) directing them to a Qualtrics survey. Participants read and view videos of the study procedures on the first page of this website. The videos have been created in Powtoon, using voiceover and images that are not related to a specific gender or race/ethnicity. After reviewing the videos, participants are provided with the informed consent document (on a subsequent page of the survey), will have the opportunity to ask questions during the live Zoom session with the research assistant. After consenting to participate, they are directed to complete the baseline survey (approximately 30-45 minutes). All participants will complete this computerized survey that assesses alcohol use, alcohol-related problems, protective behavioral strategies for drinking and their perceived effectiveness, motives and expectancies for alcohol use, anonymized social network characteristics, context of their most recent drinking occasion, marijuana and tobacco use, COVID-19 experiences, internalizing symptoms, and demographic

measures. Through a mechanism of the survey, participants are randomly assigned to one of six possible conditions regarding the timing of receiving emailed personalized feedback about their alcohol use. After completing the initial assessment, participants are then be directed to navigate through the eCHECKUP TO GO program (San Diego State University Research Foundation, 2018) until it is completed (approximately 20-30 minutes).

Subsequent assessments: Approximately 1, 3, 6, and 9 months after the initial assessment, researchers send each participant an email reminding them to complete the follow-up assessment. This email includes a link to an online follow-up survey that assesses alcohol use, related problems, protective behavioral strategies for drinking and their perceived effectiveness, anonymized social network characteristics, context of their most recent drinking occasion, and marijuana and tobacco use. If participants provide additional ways to contact them during the baseline survey (a second email address, a phone number to text), these methods are also used to send the link to the follow-up surveys.

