Boosters: After the intervention, participants receive an additional email from the researcher, depending on their study condition. For five study conditions, these emails contain personalized normative feedback about alcohol use as well as feedback about harm reduction strategies, serving as a booster to the original intervention. Baseline data are used to provide students with normative information (e.g., typical drinking among ODU students who are male/female depending on the gender of the recipient), and reminders of protective behavioral strategies they can use to reduce drinking-related harm (separated by strategies they have reported using recently versus those they might consider trying). This is received at 2 weeks, 6 weeks, 10 weeks, or 14 weeks after baseline for study conditions 1-4 respectively. This is received at all of those times for some participations (the 5th study condition). Participants in the control condition (6th study condition) do not receive any feedback via email.

Measures

The same measures are included in baseline and the follow-up surveys:

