Participants' **alcohol use** is assessed using a modified version of the Daily Drinking Questionnaire for the past 30 days (Collins et al., 1985). Additionally, participants describe specific aspects regarding their drinking in the past 30 days (e.g., highest consumption in a single day). **Descriptive Norms** are assessed by modifying the DDQ to reflect their expectations for typical male students at the same institution, typical female students at the same institution, and close friends. **Injunctive Norms** are assessed using 10 items (Carey et al., 2010). **Alcohol-related problems** are assessed using the 24-item Brief Young Adult Alcohol Consequences Questionnaire (BYAACQ; Kahler et al., 2005). **Protective behavioral strategy** (PBS) use is assessed using Sugarman and Carey's (2007) Strategy Questionnaire. **Alcohol expectancies** are assessed using the Comprehensive Effects of Alcohol questionnaire (CEOA; Fromme et al., 1993). **Motives for alcohol use** are assessed using the Drinking Motives Questionnaire (DMQ; Cooper, 1994). **Alcohol beliefs** about how salient alcohol use is to college life are assessed using the College Life Alcohol Salience Scale (CLASS; Osberg et al., 2010). Questions about their **Social media use** were created by the researcher. **Social network** and affiliated characteristics are assessed using the adapted version (DeMartini et al., 2013) of the Brief Important People

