Statistical Analysis Plan

Timing Personalized Feedback After Alcohol Health Education (TIME)

NCT04453007

11/13/2020

Statistical Analysis Plan

Prior to hypothesis testing, the data will be examined for normality and outliers. Histograms and values for skewness and kurtosis will be examined. Positively skewed variables will be natural log transformed, unless paired with an excessive number of zeroes. If there are an excess of zeroes in an outcome, the variable will be dichotomized if other values are not well represented, or appropriate modeling techniques will be used (e.g., hurdle models) if other values are well represented. Boxplots will be used to check for outliers. Extreme values will be winsorized (i.e., cases retained in the sample, but values made less extreme). Cases with missing data will be compared to complete cases across major study variables to identify if there are systematic differences in missingness. If significant associations are identified, these variables will be used as covariates in later analyses.

To address the major aim of the study, the data will be analyzed using latent growth models within a structural equation modeling framework. Separate models will be conducted for each alcohol outcome: alcohol consumption (e.g., quantity), and alcohol-related problems. It is not known the exact trajectory across time (baseline, 1 month, 3 months, 6 months, 9 months), so a few models will be compared to identify which best captures the shape of change over time. A simple model that reflects change to 1 month (slope 1; initial change post-intervention) and longer-term maintenance (slope 2; linear growth to 9 months) will be compared to models with additional piecewise slopes or curvilinear components in case longer-term maintenance is not a linear process. Study condition (6 groups) will be dummy coded across 5 variables with “no booster” as the category of reference, and will serve as a predictor of each latent variable (latent intercept, each slope). All models will be conducted using maximum likelihood estimation, and will control for gender. The model for problems will also control for alcohol quantity.

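### The 30-day drinking recall straddles the first booster at month 1 (2-week and all-times arms) and month 3 (10-week arm), so slope 1 and the month 1–3 rise mix pre- and post-booster drinking

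*Protocol*

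**What the plan says.** - **Outcome window.** Alcohol use "is assessed using a modified version of the Daily Drinking Questionnaire for the past 30 days" (Protocol, Measures). The modification is not described, so it is unknown whether students report a typical week or day-by-day totals. No recall period is given for the alcohol-problems scale.
- **Booster dates.** "This is received at 2 weeks, 6 weeks, 10 weeks, or 14 weeks after baseline for study conditions 1-4 respectively", and for the repeated-administration arm, "This is received at all of those times for some participations (the 5th study condition" (Protocol, Boosters).
- **Survey dates.** "Approximately 1, 3, 6, and 9 months after the initial assessment, researchers send each participant an email" (Protocol, Subsequent assessments). No completion window is set.
- **Model.** The SAP starts from this shape: "A simple model that reflects change to 1 month (slope 1; initial change post-intervention) and longer-term maintenance (slope 2; linear growth to 9 months". It "will be compared to models with additional piecewise slopes or curvilinear components in case longer-term maintenance is not a linear process". Condition "will be dummy coded across 5 variables with “no booster” as the category of reference", and the dummies predict the intercept and each slope.

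Neither document aligns the recall window with the email dates or treats a partly exposed survey differently from a fully exposed one.

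**The concern.** The study exists to find the best delivery time, so the early shape of each arm's curve matters. A month-1 answer describes roughly days 0 to 30, and the 2-week email arrives on day 14. Nearly half of what those students report happened before they received anything beyond the common intervention. The same happens, to a smaller degree, at month 3 in the 10-week arm. In the other arms the nominal month-1 and month-3 windows lie wholly before or wholly after the first email.

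The model takes each survey as the outcome at its time point. A booster effect that is immediate and constant would therefore appear too small at the first partly exposed survey and seem to grow by the next one. This is separate from waning, because it arises even if the effect never changes. The risk is that a recall artefact is reported as a small initial effect followed by gain during what the SAP calls longer-term maintenance, or that it shifts the ordering of timings.

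**Working it through.** The plan gives no figure of its own on this point to reproduce.

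**Inputs from the documents.** Recall length 30 days; first emails on days 14, 42, 70 and 98 (day 14 for the all-times arm); surveys at months 1, 3, 6 and 9.

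**Assumptions.** Month length 30 or 30.44 days; recall ends on the day of completion; the effect D starts at the email and stays constant; recalled days count equally.

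**Step 1: pre-booster share of the window.** Share = (first email day − (survey day − 30)) / 30, limited to 0–1.

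- Month 1, 2-week and all-times arms: 14/30 = 47% with 30-day months, 45% with 30.44-day months.
- Month 3, 10-week arm: survey on day 90, window from day 60, so 10/30 = 33%; with 30.44-day months, 29%.
- Other arms at months 1 and 3: 0% or 100%.
- Months 6 and 9: 0% in every arm. The month-6 window opens at about day 150, after the last email on day 98.

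| Completion delay | Month 1, 2-week and all-times | Month 3, 10-week |
|---|---|---|
| 0 days | 45–47% | 29–33% |
| 3 days | 35–37% | 19–23% |
| 7 days | 22–23% | 6–10% |
| 14 days | 0% | 0% |

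At 14 days late the overlap moves to other arms. With 30-day months, the 6-week arm's month-1 window becomes 7% post-booster and the 14-week arm's month-3 window 20%.

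**Step 2: measured effect.** This is (1 − share) × D. At baseline and months 1, 3, 6 and 9:

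- 2-week arm: 0, 16/30 = 0.53, 1, 1, 1 (in units of D). Undiluted: 0, 1, 1, 1, 1.
- 10-week arm: 0, 0, 0.70, 1, 1 (0.67 at month 3 with 30-day months). Undiluted: 0, 0, 1, 1, 1.

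**Step 3: the SAP's simple model.** Slope-1 loadings are 0, 1, 1, 1, 1 and slope-2 loadings 0, 0, 2, 5, 8. With independent errors the baseline value is fitted exactly, so the rest is a straight line through the four follow-ups at x = 0, 2, 5, 8 (mean 3.75; Sxx = 93 − 4 × 3.75² = 36.75). The line's intercept is slope 1.

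- 2-week, diluted: mean 0.8833; Sxy = 15 − 15 × 0.8833 = 1.75. Slope 2 = 1.75/36.75 = 0.048 D per month, or 0.38 D over months 1–9. Slope 1 = 0.8833 − 3.75 × 0.0476 = **0.70–0.71 D** (0.705). Undiluted values are 1.00 D and 0.
- 10-week, diluted: mean 0.675; Sxy = 14.4 − 15 × 0.675 = 4.275. Slope 2 = 0.116 D per month (**0.93 D** over 8 months); slope 1 = **0.24 D**.
- 10-week, undiluted: mean 0.75; Sxy = 15 − 11.25 = 3.75. Slope 2 = 0.102 D per month (0.82 D over 8 months); slope 1 = 0.37 D.

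Exchangeable errors give the same results. With autoregressive errors of 0.9 per month, the 2-week arm has slope 1 = 0.54 D and slope 2 = 0.46 D over months 1–9. For the 10-week arm the slope-2 difference then nearly vanishes (0.99 v 0.98 D).

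**Step 4: a knot at month 3.** The 2-week profile now fits exactly: slope 1 = 0.53 D, a false rise of 0.47 D from month 1 to month 3, and zero slope afterwards.

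**The case against.** **The SAP may choose a richer shape.** True, and a knot at month 3 removes the false gain after month 3 in the 2-week arm. It does not remove the dilution: slope 1 falls to 0.53 D and the false rise sits between months 1 and 3.

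**The shares are nominal.** This stands. Surveys are only approximately timed, and a week's delay roughly halves the month-1 share (slope 1 is then about 0.85 D with independent errors). The size must be given as a range. If the modified questionnaire elicits a typical week, the dilution could be larger or smaller.

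**A reader might infer that the 10-week arm is simply made to look worse.** The documents do not support that. The SAP plans no month-3 contrast between arms; it tests dummies on growth factors. The month-3 level and slope 1 are pulled down, but slope 2 is pushed up.

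**A reader might also convert the month-1 and month-3 dilution into a larger required sample.** That would hold only for single-visit contrasts. The SAP fits all five time points together, and months 6 and 9 are undiluted.

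**Months 6 and 9 are not a neutral refuge.** This also stands. At day 182 the 2-week arm is 168 days past its email and the 14-week arm 84, so waning could favour later delivery. Those comparisons belong beside the slopes, not in their place.

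**Conclusion.** The concern holds as a problem of interpretation at months 1 and 3 in three arms. At nominal dates 45–47% (2-week and all-times, month 1) and 29–33% (10-week, month 3) of the recall window is pre-booster. For a constant effect with equally weighted days, the simple model understates the 2-week arm's slope 1 by about 0.3 D (nearly 0.5 D with strong autoregression) and creates a slope-2 gain of about 0.4 D.

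The flat-effect reading fits the 2-week arm best: three later emails could produce real growth in the all-times arm. The bias in ranking timings has no single direction, and the SAP names no parameter for the ranking. Nothing can be computed for alcohol problems, because no recall period is stated. The finding does not invalidate the timing comparison; it limits what slope 1 and the early rise can be said to show.

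**What to change.** In the SAP:

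1. State that slope 1 in the 2-week and all-times arms, and any rise from month 1 to month 3 in the 2-week, all-times and 10-week arms, will not be read as the size or growth of the booster effect.
2. Add a sensitivity analysis in which booster exposure at months 1 and 3 is the share of the 30-day window after the first email, from scheduled dates. With 30-day months this is 0.53 for the 2-week and all-times arms at month 1 and 0 for the other booster arms. At month 3 it is 1 for the 2-week, 6-week and all-times arms, 0.67 for the 10-week arm (0.71 with 30.44-day months) and 0 for the 14-week arm. Repeat with actual dates only as a secondary check, because response delay arises after randomisation and may relate to drinking.
3. Report month-6 and month-9 arm differences beside the slopes, noting that time since the email differs by arm.

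The cost is some SAP wording and one additional analysis. That analysis assumes that the effect starts at the email and that recalled days count equally. Counting from the first email also ignores the later emails in the all-times arm, which should be stated. No change to treatment, surveys or questionnaires is needed.

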Statistical Analysis Plan

Timing Personalized Feedback After Alcohol Health Education (TIME)

NCT04453007

11/13/2020

Statistical Analysis Plan

Prior to hypothesis testing, the data will be examined for normality and outliers. Histograms and values for skewness and kurtosis will be examined. Positively skewed variables will be natural log transformed, unless paired with an excessive number of zeroes. If there are an excess of zeroes in an outcome, the variable will be dichotomized if other values are not well represented, or appropriate modeling techniques will be used (e.g., hurdle models) if other values are well represented. Boxplots will be used to check for outliers. Extreme values will be winsorized (i.e., cases retained in the sample, but values made less extreme). Cases with missing data will be compared to complete cases across major study variables to identify if there are systematic differences in missingness. If significant associations are identified, these variables will be used as covariates in later analyses.

To address the major aim of the study, the data will be analyzed using latent growth models within a structural equation modeling framework. Separate models will be conducted for each alcohol outcome: alcohol consumption (e.g., quantity), and alcohol-related problems. It is not known the exact trajectory across time (baseline, 1 month, 3 months, 6 months, 9 months), so a few models will be compared to identify which best captures the shape of change over time. A simple model that reflects change to 1 month (slope 1; initial change post-intervention) and longer-term maintenance (slope 2; linear growth to 9 months) will be compared to models with additional piecewise slopes or curvilinear components in case longer-term maintenance is not a linear process. Study condition (6 groups) will be dummy coded across 5 variables with “no booster” as the category of reference, and will serve as a predictor of each latent variable (latent intercept, each slope). All models will be conducted using maximum likelihood estimation, and will control for gender. The model for problems will also control for alcohol quantity.

Given prior findings that emailed booster feedback containing personalized normative feedback and protective behavioral strategies (PBS) was significantly more effective for select groups (i.e., those lower in PBS use [Braitman & Henson, 2016], legal age drinkers [Braitman & Lau-Barraco, 2018]), we will examine potential moderators of booster efficacy as a supplementary exploratory analysis. Legal drinking status by age (coded as 1 = *age 21-24* [legal], 0 = *age 18-20* [underage]) and baseline PBS use (in its original continuous metric) will be explored as potential moderators. For each outcome, two additional models will be conducted (one for each moderator). The moderator will be added as a predictor of each latent factor (latent intercept, slope 1, and slope 2). Multiple interaction terms will be created to capture the interaction with condition (dummy coded across 5 variables). These interaction terms will also be included as predictors of each latent factor. Thus, the outcome at baseline and change over time will be predicted by condition, the moderator, and the interaction between the two, controlling for relevant covariates.

References:

- Braitman, A. L., & Henson, J. M. (2016). Personalized boosters for a computerized intervention targeting college drinking: The influence of protective behavioral strategies. *Journal of American College Health, 64*(7), 509-519.
<http://doi.org/10.1080/07448481.2016.1185725>
- Braitman, A. L., & Lau-Barraco, C. (2018). Personalized boosters after a computerized intervention targeting college drinking: A randomized controlled trial. *Alcoholism: Clinical and Experimental Research, 42*(9), 1735-1747.
<http://doi.org/10.1111/acer.13815>

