online students in the study if they reported drinking alcohol with others in person. Power analyses were conducted using Monte Carlo simulation methods within Mplus (version 5.21, Muthén & Muthén). Effect sizes, variance, and covariances used were based on data from a preliminary study with similar eligibility criteria using the same booster content (Braitman & Henson, 2016; Braitman & Lau-Barraco, 2018). We estimated a retention rate of 76%, the average reported in a meta-analysis of RCTs assessing alcohol interventions for first-year college students (Scott-Sheldon et al., 2014). Monte Carlo simulation methods indicated that for the effect size expected ($b = 6.57$, $\beta = 0.537$) and for the expected 24% attrition, a sample size of $N = 180$ total students should yield sufficient power (.80+) to detect booster effects.

Recruitment Procedure

An email describing the study is sent to undergraduate students at ODU ages 18-24 who have enrolled in at least 1 credit hour, and includes a link to a screener survey. In addition to eligibility criteria (age, student status, if they drink with others, and alcohol consumed) additional irrelevant questions are included in the screener survey to discourage ineligible participants from re-taking the screener survey with different answers. Eligible participants can provide their contact information (name, email, and phone number) and are linked to Calendly to schedule their participation in the baseline protocol via Zoom.

Study Procedure

Emerging adult college drinkers are recruited via email as described above. After completing the screener to verify eligibility, participants schedule their participation time through an online time management system (Calendly). They receive an email reminder from the Calendly system 24 hours before their assigned timeslot. After participating in the fully remote baseline session via Zoom, participants are be paid \$20. They are also be invited to complete follow-up surveys for additional money. Participants are invited to complete 1-, 3-, 6-, and 9-month assessments, and receive \$10 for each completed follow-up survey. As an additional incentive, participants who complete all assessments will be given a \$10 bonus (yielding a \$70 total for the study if all follow-ups are completed). All monetary compensation is provided via online gift card to Amazon.

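### A significance test of incomplete versus complete cases chooses the covariates; at this sample size it is unreliable, and its wording does not restrict it to baseline variables

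*SAP*

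**What the plan says.** The data-preparation paragraph that opens the SAP sets out a two-step rule. First, "Cases with missing data will be compared to complete cases across major study variables to identify if there are systematic differences in missingness". Second, "If significant associations are identified, these variables will be used as covariates in later analyses". The SAP gives no significance level, no list of the major variables and no measurement occasion for them.

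The next SAP paragraph fits latent growth models by maximum likelihood over five waves. Every model controls for gender, and the problems model also controls for alcohol quantity. The exploratory moderator models also adjust for relevant covariates, so a selected variable may carry into those too.

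The protocol (Participant population) plans for 76% retention, that is, a loss of 24%, and concludes from its simulation that "a sample size of $N = 180$ total students should yield sufficient power (.80+) to detect booster effects".

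**The concern.** Two features of the rule are weak.

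- **Selection by significance.** Whether a variable helps to correct for dropout depends on its relation to both missingness and the outcome, not on whether a test in a small sample reaches 0.05. With few incomplete cases, real correlates will often fail the test and some unrelated variables will pass it. The covariate set is then unknown until the outcome data are in hand.
- **No restriction to baseline.** Drinking, problems and protective strategies are measured again at every follow-up (protocol, Subsequent assessments), and the boosters target drinking and strategy use (protocol, Boosters). If a follow-up value passed the screen and became a covariate, the model would condition on something that some arms' boosters could already have changed and other arms' could not. The trial's aim is to compare delivery times, so an error that differs by delivery time falls on the main question.

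**Working it through.** **Inputs.** N = 180 and 24% attrition come from the protocol. The 0.05 two-sided level is assumed, since the SAP states none. The protocol's N = 180 cannot be reproduced, because the variances, covariances and target parameter behind its simulation are not printed. This point uses only N and the attrition rate.

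**Step 1: size of the screen.** 180 × 0.24 = 43.2 incomplete and 180 × 0.76 = 136.8 complete, so about 43 versus 137. With four follow-ups, the share with any missing data could exceed 24%. An assumed 40% gives 72 versus 108.

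**Step 2: power of the screen.** Two-sample t-test with 178 degrees of freedom and noncentrality d / √(1/n₁ + 1/n₂). The square root is 0.1748 for 43 versus 137 and 0.1521 for 72 versus 108.

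| True difference d | Noncentrality, 43 v 137 | Power | Noncentrality, 72 v 108 | Power |
|---|---|---|---|---|
| 0.2 | 1.14 | 21% | 1.31 | 26% |
| 0.3 | 1.72 | 40% | 1.97 | 50% |
| 0.4 | 2.29 | 62% | 2.63 | 74% |
| 0.5 | 2.86 | 81% | 3.29 | 90% |

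The difference found with 80% power at 43 versus 137 is about (1.96 + 0.84) × 0.1748 = 0.49. If three independent variables each truly differed by 0.3, all three would be flagged with probability 0.40³ = 0.064, about 6%.

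**Step 3: chance entries.** For k independent unrelated variables, the probability of at least one false entry is 1 − 0.95^k: 40% for k = 10 and 54% for k = 15. The values of k are assumptions. The protocol's Measures section lists about 18 constructs before demographics, but the SAP does not say which count as major. Positive correlation among them would normally lower these figures.

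**Step 4: when an omitted predictor matters.** Suppose X predicts the outcome with slope γ, the same in every arm. In a completers-only comparison, the expected arm contrast is

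true effect + γ × (mean of X among completers in the booster arm − mean of X among completers in control).

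If X drives dropout in the same way in both arms, the bracket is zero and so is the bias. If it does not, bias appears. For example, with assumed γ = 0.5 and a completer difference of −0.1 SD, a true −0.40 becomes −0.40 − 0.05 = −0.45. If γ itself differs by arm, the contrast also shifts, because the completers' mix differs from that of everyone randomised.

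**Step 5: status of a follow-up variable, by arm.** Boosters go out at weeks 2, 6, 10 and 14. One month is about week 4 and three months about week 13.

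| Arm | 1-month value | 3-month value |
|---|---|---|
| Week 2 | post-booster | post-booster |
| Week 6 | pre-booster | post-booster |
| Week 10 | pre-booster | post-booster |
| Week 14 | pre-booster | pre-booster |
| All four times | after the first booster | after three boosters |
| Control | no booster | no booster |

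In a simple linear model, adjusting for such a variable leaves roughly (total effect − λδ). Here λ is the variable's coefficient given arm, and δ is the arm's booster effect on it by that wave. For an arm not yet boosted, δ = 0 and nothing is removed; for an arm already boosted, λδ is removed. Neither λ nor δ is in the documents, so the asymmetry can be shown but not its size.

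**The case against.** **Follow-up covariates are not planned in so many words.** This stands. No sentence in either document says that a follow-up value will become a covariate. Baseline is the only wave every randomised person is expected to have, so it is the natural basis for the comparison. A baseline-only check may well be what the sponsor means. What remains is that the rule does not say so, although the SAP does specify baseline when it defines the strategy-use moderator.

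**A reader might infer that 1-month drinking would be admitted and would remove half or more of the week-2 effect.** The documents do not support that. A loss of that size comes from a plain regression of later drinking on arm and 1-month drinking, with an assumed correlation and equal effects at both times. The planned consumption model is a growth model in which 1-month consumption is already one of the five waves. More plausible entrants are follow-up strategy use, or follow-up drinking in the problems model, and no size can be given for those.

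**A reader might also infer that a missed predictor necessarily leaves attrition bias in the arm contrasts.** Step 4 shows that it need not. In addition, maximum likelihood over all waves, if every available observation is used, already accounts for dropout related to observed drinking. The SAP does not state that all available data are used, but this is usual for such models.

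**The predictors most often missed are the weak ones, and a baseline variable admitted by chance does not bias a randomised contrast.** Both are correct. Even so, a moderate predictor (d = 0.3) is missed more often than not at 43 versus 137, and the covariate set still depends on the data.

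**Conclusion.** The point holds in a limited form. The SAP's rule makes the adjustment set depend on an underpowered test. At the planned size, a true difference of 0.3 is missed about 60% of the time, and one of about 0.5 is found about 80% of the time. If 40% of cases are incomplete, the 0.3 difference is missed about half the time. These figures assume a two-sided 0.05 level.

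No bias in the timing contrasts has been demonstrated. Omission matters mainly if dropout, or the predictor's effect, differs by arm. The follow-up route to bias depends on an occasion that the SAP leaves unstated. If that route were taken, the distortion would fall unequally on the delivery-time arms, by an amount that cannot be derived from the documents. This is a cheap improvement to the SAP rather than a defect that undermines the trial.

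**What to change.** Rewrite the end of the data-preparation paragraph as follows.

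1. Delete the rule that a significant difference makes a variable a covariate.
2. Name in advance a short, fixed set of baseline variables: for example strategy use, legal-age status and student status, plus baseline consumption or problems where these are not already a wave or a covariate of the model in question.
3. Include that set as auxiliary variables under full-information maximum likelihood in every model, whatever the p-values, and state that all available observations are used.
4. State that no post-randomisation variable may become a predictor of the growth factors through the missingness check.
5. Keep the comparison of incomplete and complete cases as description only.

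**Cost.** One paragraph of the SAP and no new data, since all these variables are already collected. Each auxiliary variable adds some parameters (its covariances with the five waves and the predictors), so at N = 180 the set should stay short.
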